#### **6.1.9.1 Assessment of Major and Clinically Relevant Non-major Bleeding**

Bleeding will be defined using the International Society of Thrombosis and Hemostasis definition of major bleeding for clinical investigations of anti-hemostatic medicinal products in nonsurgical patients (i.e., fatal bleeding, critical organ bleeding such as CNS bleeding, or bleeding causing a fall in hemoglobin of 20 g/L or more) and clinically relevant non-major bleeding (i.e., bleeding that does not fit the former definition of major bleeding but prompts medical attention).

### **6.2 LABORATORY PROCEDURES AND EVALUATIONS**

All laboratory procedures and evaluations will occur at times indicated in Section 6.9, Schedule of Events.

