#### **6.1.9 ADVERSE EVENT EVALUATION**

Toxicities and adverse experiences will be assessed at each visit using the [CTCAE v5.0](#).

Safety will be monitored by assessing physical examination, vital signs, and weight, performance status, hematology, chemistry, coagulation, and pregnancy, as well as collecting of the AEs and medications at study visits.

Adverse events will be monitored from the time the participant signs the informed consent form, but will not be included for analysis if occurring before the study agent is given. Participants will be instructed to report all AEs during the study and will be assessed for the occurrence of AEs throughout the study. All AEs (serious and non-serious) must be recorded in the medical record and (e)CRFs regardless of the assumption of a causal relationship with the study drug; however, known AEs associated with a participant's planned anticancer treatment regimen will not be collected except for the development of grade 3-4 thrombocytopenia. For details on AE collection and reporting, refer to Section 7, Safety.

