## **6.8 UNSCHEDULED VISITS**

Unscheduled study visits may occur at any time if medically warranted. Any assessments performed (e.g., laboratory or clinical assessments) at those visits should be recorded in (e)CRF.

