	Days -28 to -3	Day 1		
			F AEs and laboratory safety measurements will be graded per NCI CTCAE version 5.0. All AEs, whether gradable by CTCAE or not, will also be evaluated for seriousness. Report grade 3 and 4 hematological and non-hematological SAEs (related and unrelated to trial treatment) occurring up until 60 days after catheter placement. AE evaluation includes assessment of major and clinically-relevant non-major bleeding per Section 6.1.9.1.	
			G Study visit to occur within 24hrs or day of single dose of study treatment. If screening visit occurs within 24hrs of study treatment administration, D1 provider visit does not need to be repeated.	
			H Blood will be collected and batched on day 14 for Immunogenicity assessment. The Day 1 blood draw should be obtained any time prior to study drug administration.	
			I Electrocardiogram will be obtained at screening and as clinically indicated.	

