#### 8.2.3 ANALYSIS OF THE SECONDARY ENDPOINTS

The incidence of major or clinically relevant non-major bleeding (defined in Section 6.1.9.1), along with 95% CI, will be assessed using the safety analysis set. The proportion of safety set participants with these bleeding events will also be separately estimated for each catheter type.

The incidence of xisomab 3G3-associated toxicities will be assessed using the safety analysis set. Descriptive statistics of safety will be presented using CTCAE v5.0. All on-study AEs (from time of consent), treatment-related AEx (from time of xisomab infusion), SAEs, and treatment-related SAEs will be tabulated using worst grade per NCI CTCAE v5.0 criteria by system organ class and preferred term. On-study abnormal lab parameters including hematology, chemistry, liver function, and renal function will be summarized using worst grade NCI CTCAE v5.0 criteria.

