#### 8.2.4 ANALYSIS OF THE EXPLORATORY ENDPOINTS

Descriptive statistics will be used to present results of coagulation measures (i.e., platelet count, PT/INR, and aPTT), drug PK, and incidence of catheter occlusion requiring medical therapy (specifically, local administration of tPA). The proportion of participants with symptomatic thrombosis by Day 18 and the median (and range) time from xisomab infusion to clot symptoms

will be reported for those (expected few) participants with symptomatic CAT. All exploratory endpoints will additionally be analyzed within each catheter type (i.e., PICC vs. indwelling central venous catheter).

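### Hematology and biochemistry are scheduled only before dosing, yet the plan monitors safety by them and summarizes on-study results by worst grade

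*Combined protocol and SAP*

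**What the plan says.** Section 6.2 sends the timing of every laboratory test to the schedule: "All laboratory procedures and evaluations will occur at times indicated in Section 6.9, Schedule of Events". In the Section 6.9 table the Hematology and Biochemistry rows carry a single mark, under Screening. The Coagulation row carries two, at screening and at the Day 14 (±4) end-of-treatment visit, and Section 6.2.3 confirms the second in prose. Sections 6.2.1 and 6.2.2 list what the CBC and the metabolic panel contain but give no time points.

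Several other sections need post-dose values:

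- Section 6.1.9: "Safety will be monitored by assessing physical examination, vital signs, and weight, performance status, hematology, chemistry, coagulation, and pregnancy".
- Section 6.1.9 also says that known adverse events of the anticancer regimen "will not be collected except for the development of grade 3-4 thrombocytopenia".
- Section 6.9, footnote F: "AEs and laboratory safety measurements will be graded per NCI CTCAE version 5.0".
- Section 8.2.3: "On-study abnormal lab parameters including hematology, chemistry, liver function, and renal function will be summarized", by worst CTCAE grade.
- Section 8.2.4 counts platelets among its exploratory measures: "coagulation measures (i.e., platelet count, PT/INR, and aPTT".
- Section 6.1.9.1 includes in major bleeding "bleeding causing a fall in hemoglobin of 20 g/L or more".

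Part of the gap is covered. For unscheduled visits, Section 6.8 says: "Any assessments performed (e.g., laboratory or clinical assessments) at those visits should be recorded in (e)CRF". Section 7.2.1 lists clinically significant laboratory abnormalities among adverse events.

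**The concern.** Safety is the secondary objective of this trial of an anticoagulant antibody, and Section 1.4.1 says its safety profile in humans is not yet settled. Section 5.1 lets chemotherapy start two days after the dose, so platelets may fall while the drug is still active. Section 1.3 reports a prolonged aPTT at Day 14 in the phase 1 trial.

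Followed as written, the plan produces no required platelet count, hemoglobin, liver or renal value after dosing. The laboratory summaries would then describe only participants whose treating team happened to order a test, and only results that reached the case report form. A participant with an unnoticed low platelet count and no test would add no thrombocytopenia event to the adverse event tables. The likely direction of error is therefore towards too few laboratory toxicities.

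**Working it through.** The plan gives no figure for this point, so the check sets the schedule against the sections that depend on it.

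**1. Does every scheduled CBC and metabolic panel precede the dose?** Screening covers Days -28 to -3 (Section 6.9). Catheter placement defines Day 1, and the dose falls within 2 days either side of it (Section 5.1). The earliest dose is therefore two days before Day 1, which is after Day -3 whether or not a Day 0 is counted. The answer is yes.

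**2. Scheduled clinical laboratory panels per participant (Section 6.9)**

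| Panel | Screening | Day 1 | Day 14 (±4) | Day 60 | Total after dosing |
|---|---|---|---|---|---|
| Hematology (CBC) | 1 | 0 | 0 | 0 | 0 |
| Biochemistry (CMP) | 1 | 0 | 0 | 0 | 0 |
| Coagulation (aPTT, INR) | 1 | 0 | 1 | 0 | 1 |

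Over 50 participants that is 50 × 0 = 0 scheduled post-dose CBCs and 50 × 0 = 0 scheduled post-dose metabolic panels. A table misread in extraction is unlikely, because the Coagulation row keeps its Day 14 mark and Section 6.2.3 agrees with it.

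**3. Could another scheduled sample fill the gap?** The research draw is a citrate tube for coagulation and PK work (Section 6.3), with immunogenicity added by footnote H of Section 6.9. It is not a CBC or a metabolic panel. Day 60 follow-up may be by phone or chart review (Section 6.7).

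**4. Could the screening sample serve?** Sections 6.1.9 and 6.4 leave events before dosing out of the analysis. Even if on-study in Section 8.2.3 were read as starting at consent, a screening value cannot show an effect of the dose.

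**5. Which unscheduled results must be captured?** Section 6.8 covers tests done at unscheduled study visits. Section 7.2.1 covers abnormalities judged clinically significant. Section 6.2.3 extends capture to other clinically indicated tests, but only for coagulation; Sections 6.2.1 and 6.2.2 have no such sentence. A normal routine CBC has no stated route into the data, so the number of participants tested may be lost along with the result.

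**The case against.** The strongest reply is that the plan relies on routine oncology care by choice. Section 6 asks that study laboratory work be done at standard-of-care visits where possible, and Section 6.2.1 collects the CBC by institutional standards. Patients receiving chemotherapy usually have counts taken. Section 7.5 has the investigator ask about adverse events at each visit, and chart review at Day 60 may reveal results. Entry criteria limit the risk: platelets must exceed 100 × 10⁹/L, and chemotherapy with a 15% or higher incidence of grade 3-4 thrombocytopenia is excluded. Platelet count is not named as an endpoint in Section 2.2. With chemotherapy starting soon after the dose and no control arm, a Day 14 count could not separate drug from chemotherapy effects.

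Much of this stands, and it limits the severity. It does not supply a required or timed post-dose test, nor a rule for capturing routine results. CTCAE-graded toxicity is an endpoint in Section 2.2.2, and Section 8.2.3 promises the laboratory summary. Difficulty with attribution does not remove the need to ascertain events.

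Three stronger readings are not supported:

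- A reader might infer from the hemoglobin criterion that the bleeding endpoint is compromised. Section 6.1.9.1 requires bleeding first, and a bleed that prompts medical attention counts as clinically relevant non-major without any hemoglobin value. Section 8.2.3 analyzes major and clinically relevant non-major bleeding as one incidence. A missing hemoglobin mainly risks the label. An event would leave the combined incidence only if it prompted no medical attention and met no other major criterion.
- A reader might infer that untested participants will be counted as normal in the laboratory summary. Section 8.4 rules out imputation and requires the sample size of each analysis, with reasons for exclusion.
- A reader might infer that no post-dose counts will exist. Sections 6.8 and 7.2.1 capture some, and routine testing is likely.

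**Conclusion.** The mismatch is real: hematology and biochemistry are scheduled only before dosing, while safety monitoring and the worst-grade summaries depend on values after it. The consequence is possible under-ascertainment of asymptomatic laboratory toxicity, chiefly thrombocytopenia, in descriptive safety tables. The primary endpoint does not use these tests, and the combined bleeding incidence is little affected.

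The size of the loss cannot be calculated from the documents, because they do not say how many participants will have routine post-dose tests. As written, the number with a captured post-dose CBC could lie anywhere from 0 to 50. Section 8.2.3 plans no confidence interval for the laboratory summary, so limits based on guessed numbers tested would add nothing. Section 8.4 would disclose sparse data but would not supply the missing values. The conclusion assumes that the Section 6.9 table is followed as printed. The change is worth making because it is cheap and improves safety ascertainment.

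**What to change.** 1. **Section 6.9:** mark Hematology (CBC with platelets) at the Day 14 (±4) visit, with the existing coagulation draw. Mark Biochemistry (CMP) there too, or else limit the chemistry, liver and renal summary in Section 8.2.3 to clinically obtained results and say so.
2. **Sections 6.2.1 and 6.2.2:** add a capture sentence on the model of Section 6.2.3, for example: *Results obtained as clinically indicated after dosing, through the end of the adverse event recording period (Day 60 or start of alternative anticoagulation), will also be captured.*
3. **Section 8.2.3:** state that the denominator for each laboratory worst-grade summary is the number of participants with at least one post-dose result for that panel. This makes the general rule in Section 8.4 specific.

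The cost is up to 50 × 1 = 50 CBCs and, if that option is taken, 50 metabolic panels, all at a visit that already draws blood, plus some abstraction of routine results. One Day 14 sample will not catch every nadir, so the timed sample and the capture rule are both needed. The sample size and the primary endpoint do not change.

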#### **6.2.1 HEMATOLOGY**

A complete blood count (CBC) with differential will be collected, per institutional standards, and should include : RBC, hematocrit, hemoglobin, platelet, white blood cell (WBC), and WBC differential.

#### **6.2.2 BIOCHEMISTRY**

Comprehensive metabolic panel (CMP), including: Na, K, Cl, CO2, BUN, Creatinine, Ca, Glucose, Albumin, Total protein Alkaline Phosphatase, total bilirubin, aspartate aminotransferase (AST), and alanine aminotransferase (ALT).

#### **6.2.3 COAGULATION PANEL**

Activated Partial Thromboplastin Time (aPTT) and pro-thrombin time (INR) are required at screening (baseline) and on Day 14 ( $\pm$ 4 days) study visit. Results from any other coagulation test performed as clinically indicated will also be captured.

#### **6.2.4 ECHOCARDIOGRAM**

Required only as clinically indicated.

#### **6.2.5 PREGNANCY TEST**

For women of childbearing potential, a serum or urine pregnancy test will be done within 72 hours prior to receiving study drug. If the urine pregnancy test is positive, a serum pregnancy test must be performed per institutional standards.

## 6.3 EXPLORATORY STUDIES

Research blood specimens will be collected for additional coagulation studies (e.g., PT/INR, and aPTT) and drug PK evaluation.

### *i) Collection of Specimens*

The research blood draws will occur as noted in Section 6.9, Schedule of Events. The research blood draw should be collected in a blue top (3.2% sodium citrate) tube. Collection of research blood should occur before collection of samples in additive-containing tubes such as the EDTA, heparin, or clot activator tubes.

### *ii) Transport of Specimens*

Within 3 hours from time of collection, whole blood research samples should be transported at room temperature to [name] Laboratory:

[name],  
[name]

### *iii) Handling of Specimen*

Whole blood samples should be centrifuged at a speed of 1500g for at least 15 minutes to achieve platelet poor plasma. Plasma is to be transferred into a polypropylene vial being careful to avoid the buffy coat. Specimens can be stored at -70°C until ready for analysis.

### *iv) Site Performing Studies*

Coagulation assays will be performed in the investigator's laboratory.

## 6.4 SCREENING AND BASELINE ASSESSMENTS

A screening (consultation) visit may occur as part of standard of care. If a participant is eligible for the study after review of key inclusion/exclusion criteria, additional screening and/or baseline visits will be scheduled while staff members are requesting insurance authorization to participate in a clinical trial. The following will be reviewed at initial screening visit:

- Clinical history and physical exam (per standard of care)
- Informed consent obtained and documented

Toxicities which occur prior to the start of treatment will not be subject to analysis. Consent must be obtained before initiation of any clinical screening procedures that are performed solely for the purpose of determining eligibility for this research study. Evaluations performed as part of routine care before informed consent can be utilized as screening evaluations if done within the defined time period.

## 6.5 ASSESSMENTS DURING TREATMENT

Specific on-study assessments are listed in the Section 6.9, Schedule of Events. Visits should occur on Day 1 and Day 14 ( $\pm 4$  days). The Day 14 ( $\pm 4$  days) visit will include an ultrasound, as well as corresponding history and physical exam. The presence of CAT, either symptomatic or asymptomatic, at time of assessment should be recorded in (e)CRF.

For all other assessments: under certain circumstances (e.g., clinic holiday, inclement weather) scheduled visits may be delayed by no more than 4 days, or may occur earlier than scheduled by no more than 4 days.

## **6.6 END OF TREATMENT VISIT**

An end of treatment visit should occur on Day 14 ( $\pm 4$  days) after catheter placement and include assessments listed in Section 6.9, Schedule of Events.

If a participant does not reach the end of treatment due to transition to hospice or death, an end of treatment visit will not be conducted.

### **6.6.1 EARLY TERMINATION VISIT**

Participants should be evaluated within 10 days after terminating participation, or evaluated prior to the initiation of any other off-study interventional therapy. Early termination assessments are listed in the Section 6.9, Schedule of Events.

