### **3.6 PARTICIPANT WITHDRAWAL OR DISCONTINUATION**

Participants are free to withdraw consent and discontinue participation in the study at any time and without prejudice to further treatment.

If a participant withdraws consent, they will be specifically asked if they are withdrawing consent to:

- All further participation in the study including any further follow up
- Withdrawal of consent to the use of their study generated data
- Withdrawal to the use of any biological samples

No further participant contact should be made if the participant withdraws consent for participation in the study. Information about the reason(s) for discontinuation and collection of any new or ongoing AEs and medications should be collected at the time the participant withdraws consent.

For all other reasons for discontinuation from the study treatment phase, the participant should return to the clinic for the end of treatment (EOT) visit according to Section 6, Study Procedures/Evaluations And Schedule

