## 6.9 SCHEDULE OF EVENTS

Visit Days*	Screening**	On-Study Treatment	End of Treatment Visit Day 14 ( $\pm 4$ days)	Follow-Up Day 60 ( $\pm 4$ days)
	Days -28 to -3	Day 1		
Informed consent	X			
Inclusion/exclusion criteria	X			
Catheter placement A		X		
Xisomab 3G3		X		
Medical history	X			
Medication history	X			
Physical Examination C	X	X G	X	
Radiographic Imaging		Per investigator's discretion, as clinically indicated		
Ultrasound D			X	
Hematology	X			
Biochemistry	X			
Coagulation	X		X	
Pregnancy test E	X			
AE assessment and Conmeds B,F	X	X	X	X
Research blood draw/Assessment for Immunogenicity H	X	X	X	
Electrocardiogram I	X	As clinically indicated		

\* Ideally the clinic visit and all the study requirements should be performed as indicated.

\*\* Enrolled participants will receive a single fixed dose of xisomab 3G3 (2 mg/kg) through a peripheral IV or the inserted catheter within 48 hours of catheter placement (i.e.  $\pm 2$  days). If Xisomab 3G3 is administered prior to D1 catheter placement, eligibility must be confirmed prior to study drug administration.

A Placement of the catheter in participants will be performed according to institutional guidelines. Ultrasound may be used to guide the placement of the catheter, and may include use of local anesthetic.

B For concomitant medications – enter new medications started during the trial through the end of treatment visit.

C All physical exams will include assessing vital signs, weight and ECOG performance status.

D Per institutional standards, study participants will be evaluated for CAT via planned ultrasound 14  $\pm 4$  days after catheter insertion. Additional ultrasound evaluations may occur at any time during the study based on treating physician and PI discretion; however, only ultrasounds performed within 18 days from catheter placement will be included when computing CAT incidence. Ultrasound to occur as part of EOT, prior to provider visit.

E For women of reproductive potential, a serum pregnancy test should be performed within 3 days prior to first dose of trial treatment. Serum pregnancy test should be performed by the local study site laboratory per institutional guidelines, and repeated if required.

Visit Days*	Screening**	On-Study Treatment	End of Treatment Visit Day 14 ( $\pm 4$ days)	Follow-Up Day 60 ( $\pm 4$ days)

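### Section 6.6.1 relies on early termination assessments that Section 6.9 does not list, and its 10-day window is neither tied to the Day 18 endpoint limit nor reconciled with Section 3.6

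*Combined protocol and SAP*

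**What the plan says.** Section 6.6.1 sets the timing of the early termination visit: "Participants should be evaluated within 10 days after terminating participation, or evaluated prior to the initiation of any other off-study interventional therapy". For its content it says: "Early termination assessments are listed in the Section 6.9, Schedule of Events".

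The Section 6.9 table has four visit columns: Screening, Day 1, EOT (headed "End of Treatment Visit Day 14", with a margin of 4 days either side) and Follow-Up at Day 60. Ultrasound is marked only under EOT. Footnote D adds that "only ultrasounds performed within 18 days from catheter placement will be included when computing CAT incidence".

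Section 3.6 treats stopping differently according to the reason. After withdrawal of consent: "No further participant contact should be made if the participant withdraws consent for participation in the study". For any other reason for leaving the treatment phase, "the participant should return to the clinic for the end of treatment (EOT) visit according to Section 6". Section 6.6 times that visit: "An end of treatment visit should occur on Day 14", again with the 4-day margin, so Day 10 to Day 18.

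For the analysis, Section 8.1 admits to the efficacy set only participants with an ultrasound and a physical exam no later than Day 18, and Section 8.2.2 uses that set for the primary endpoint. Section 8.4 rules out imputation. Section 3.6.1 provides replacements only for participants who withdraw before dosing.

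**The concern.** The drug is given once. A participant who stops after dosing has had the full exposure and can still supply the primary outcome, which needs one scan and one exam. The early termination rule is where the protocol should secure that outcome, and it does not. It names no ultrasound, because the list it refers to is missing, and its time limit runs from the day of stopping rather than from the endpoint cut-off.

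At stake is exclusion from the primary analysis for reasons that may be related to catheter-associated thrombosis (CAT) risk. People who stop because they are unwell or are moving to other treatment need not have average risk. With a single arm read against an assumed 60% rate, no control group would share the loss or reveal it.

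**Working it through.** **1. The cross-reference.** I looked in Section 6.9 for anything that could serve as the early termination list.

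| Element of 6.9 | Mentions early termination? | Ultrasound marked? |
|---|---|---|
| Screening | No | No |
| Day 1 | No | No |
| EOT, Day 14 ± 4 | No | Yes |
| Follow-Up, Day 60 ± 4 | No | No |
| Footnotes A to I | No | D limits which scans count |

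The header row appears twice with the same four columns, so this is not a table broken in extraction.

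**2. The window.** Inputs: a limit of 10 days after stopping (6.6.1), Day 1 as the day of insertion (3.5), and the Day 18 cut-off (8.1). If a participant stops on day t, the latest visit that meets the 10-day limit is t + 10. This passes Day 18 when t + 10 > 18, that is, t ≥ 9. The window t to t + 10 holds 11 days, of which t − 8 are too late.

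| Stops on day | Latest visit | Days of the window after Day 18 |
|---|---|---|
| 8 | 18 | 0 of 11 |
| 9 | 19 | 1 of 11 |
| 10 | 20 | 2 of 11 |
| 14 | 24 | 6 of 11 |
| 18 | 28 | 10 of 11 |

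If footnote D's 18 days are counted as elapsed days from insertion, the last countable day is Day 19 and the problem starts at t = 10. The alternative in 6.6.1, a visit before other off-study therapy, has no day limit at all.

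**3. Can 3.6 and 6.6.1 both be met?** Yes. For every t from 1 to 18 the window overlaps Days 10 to 18: t = 1 gives Days 1 to 11, which share Days 10 and 11, and t = 18 gives Days 18 to 28, which share Day 18. The rules are compatible, but 6.6.1 can be met on a day that does not satisfy 3.6, and no text says which governs.

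**4. The plan's sample size.** Inputs from 8.3.1: p0 = 0.60, p1 = 0.40, two-sided α = 0.05, power 80%, 4% ineligible.

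n = [(1.960 × √0.24 + 0.842 × √0.24) / 0.20]² = 47.09, rounded up to 48. Then 48 / 0.96 = 50, which reproduces the plan. The allowance is 4% × 50 = 2 participants for all causes together.

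**5. Power if more are lost.** The documents give no early termination rate, so the counts below are an assumed range. Power = Φ(0.20 / √(0.24/n) − 1.960).

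| Lost of 50 | Evaluable | Power |
|---|---|---|
| 2 | 48 | 80.7% |
| 3 | 47 | 79.9% |
| 5 | 45 | 78.2% |
| 8 | 42 | 75.4% |

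An exact binomial test (one tail 0.025) gives 75.3% at 48 and 79.0% at 47. That sequence is not monotone in n, so it shows no power cost from a third loss either.

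**6. Room for bias.** If all 50 are dosed and m have no outcome, the incidence over all 50 lies between x/50 and (x + m)/50, where x is the number of CAT events seen. The gap is m/50, or 2 percentage points per missing participant: 6 points for m = 3 and 10 for m = 5. These are outer bounds, not expected bias.

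**The case against.** The strongest reply is that the protocol read as a whole does schedule the scan. Section 3.6 sends everyone who stops for a reason other than consent withdrawal to the EOT visit, and 6.9 assigns that visit the ultrasound. A participant seen only after Day 18 has not been handled as 3.6 asks. This stands in part. A reader might infer that a participant can satisfy the whole protocol and still lose the scan, and the documents do not support that. But 3.6 itself defers to Section 6, where 6.6.1 is the specific early termination rule placed under the EOT heading. A coordinator who follows it has no instruction to scan by Day 18.

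Three further objections stand:

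- A reader might infer that every termination from Day 9 to Day 18 is lost. Anyone already scanned in the EOT window, or earlier because of symptoms, loses nothing.
- A reader might infer that 6.6.1 orders the recall of participants who withdrew consent. It is merely silent, and 3.6 is explicit. No endpoint data turn on this.
- The recoverable group is small. Most off-study reasons in 3.7 (refusal of follow-up, loss to follow-up, death) cannot be recovered, and 6.6 waives the visit for hospice or death. Investigator's discretion is the main reason left.

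**Conclusion.** The point holds in a limited form. The early termination list is missing, and the 6.6.1 window can end after the last day on which a scan counts. The loss arises only for dosed participants who stop from about Day 9 or 10, have not been scanned, would have accepted a scan, and are handled under 6.6.1 rather than 3.6.

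The number is probably small, and the documents give no rate from which to estimate it. A reader might infer that a few such losses leave the trial underpowered. One loss beyond the allowance costs under 1 percentage point by the normal approximation, so power is not the argument. Nor do the documents show which way any bias would run. What remains is avoidable and possibly selective loss of the primary outcome. It is worth correcting because the correction costs almost nothing.

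**What to change.** - In 6.9, relabel the EOT column 'EOT / Early Termination', so that the reference in 6.6.1 has a target.
- Reconcile 6.6.1 with 3.6. Ask dosed participants who stop for any reason short of full consent withdrawal to keep the ultrasound and exam in the Day 14 ± 4 window, and in any case by Day 18. Leave later safety assessments allowed.
- State that 6.6.1 does not apply to participants who withdraw consent to all contact.
- Add an analysis rule for early scans. Section 8.1 sets no earliest day, so a negative scan before Day 10 would now count as a full 18-day outcome. Section 1.1 puts the mean time from insertion to thrombosis at 8 to 11 days, so such a scan can miss later clots and bias the incidence downward. If only a scan before Day 10 can be obtained, record it, do not count a negative result as CAT-free through Day 18 in the primary analysis, and report it in a sensitivity analysis.

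The cost is minor protocol edits and one small sensitivity analysis. No procedure is added beyond those every participant already has.
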